5.2 EXCLUSION CRITERIA

1. Known allergy to Vitamin C
2. Inability to obtain consent
3. Age < 18 years
4. No indwelling central or peripheral venous or arterial catheter in patients requiring insulin in a manner that requires glucose being checked more than twice daily (e.g. continuous infusion, sliding scale)
5. Presence of diabetic ketoacidosis
6. Patient or surrogate or physician not committed to full support (not excluded if patient would receive all supportive care except for cardiac resuscitation);
7. Pregnancy or breast feeding (as documented by urine or serum pregnancy testing)
8. Moribund patient not expected to survive 24 hours
9. Active or history of kidney stone
10. History of chronic kidney disease, stage IIIb or above
11. History of glucose-6-phosphate dehydrogenase (G6PD) deficiency
12. Active malignancy, except non-melanoma skin cancer
13. Uncontrolled upper or lower gastrointestinal bleeding
14. Possible alcoholic hepatitis or other confounding cause of acute hepatitis such as viral, metabolic, autoimmune
15. History of decompensated cirrhosis as indicated by variceal bleeding within 3 months, tense ascites, or hepatocellular carcinoma (HCC)
16. History of liver or other organ transplantation
17. Initial ALT or AST greater than 5 times the upper limit of normal
18. Positive urine or serum toxicology screen and acetaminophen level
19. Non-English speaking
20. Ward of the state (inmate, other)

5.3 LIFESTYLE CONSIDERATIONS

Not applicable to this study.

5.4 SCREEN FAILURES

Screen failures are defined as participants who consent to participate in the clinical trial but are not subsequently randomly assigned to the study intervention or entered in the study. A minimal set of screen failure information is required to ensure transparent reporting of screen failure participants, to meet the Consolidated Standards of Reporting Trials (CONSORT) publishing requirements and to respond to queries from regulatory authorities. Minimal information includes demography, screen failure details, eligibility criteria, and any serious adverse event (SAE). Subjects will be documented in the Study Screening Log when all Inclusion Criteria are met.

Individuals who do not meet the criteria for participation in this trial (screen failure) because of exclusion criteria such as failure to obtain consent, inability to locate LAR, or delay in diagnosis may be rescreened. Rescreened participants should be assigned the same participant number as for the initial screening.

5.5 STRATEGIES FOR RECRUITMENT AND RETENTION

Patients with sepsis and AH will be recruited from the Emergency Department (ED), the medicine inpatient Digestive Health Service (DHS), and the intensive care units (ICU) at Virginia Commonwealth University Health System (VCUHS). VCUHS is a large tertiary care medical center with a large referral base. Annually over 11,000 patient contacts are made for liver disease and 15% of these are for alcohol related liver disease. Study personnel will review patients within the electronic medical record to identify potential candidates for enrollment. Permission to approach patients and/or their families will be requested from the attending physicians in charge of patient care in the ED, inpatient unit (DHS), or the ICU. All patients meeting the inclusion/exclusion criteria will be approached with a consent and will be entered into a screening log. If the patient is not enrolled, the screening log will include information explaining why enrollment did not occur (exclusion criteria, attending physician denial, patient refusal, etc.). If a patient is enrolled in the ICU and meets ICU discharge criteria based on the decision of the ICU attending physician, the patient will be transferred to the DHS inpatient team on Main 9 West (M9W) unit in order to continue the study drug infusion.

6 STUDY INTERVENTION

6.1 STUDY INTERVENTION(S) ADMINISTRATION

6.1.1 STUDY INTERVENTION DESCRIPTION

All study drug doses will be administered via central or peripheral line infusion. Should no central or peripheral line be available at scheduled time of infusion, a call should be placed to pharmacy to determine if study drug may be piggybacked into the line that is infusing a different drug. If administering study drug via piggyback is contraindicated, then study drug infusion may be delayed by a maximum of 6 hours. If clinical drug administration schedule is such that study drug will not have an available administration time beyond this delay, a dedicated new line (peripheral or central) should be inserted. Study drug will be blinded using an identical appearing placebo.

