2.3 RISK/BENEFIT ASSESSMENT

2.3.1 KNOWN POTENTIAL RISKS

Potential Physical Risks of Ascorbic Acid Infusion: dry mouth, nausea, vomiting, dizziness, headache, pseudohyperglycemia (if checked with point of care glucose testing), crystalluria.

Potential Psychological, Social, Legal Risks of Ascorbic Acid Infusion: No psychological, social or legal risks are identifiable from an extensive literature search.

Risks of Blood Draws: All patients will have blood drawn for research purposes. Most blood will be drawn through indwelling catheters. Risks of drawing blood percutaneously are uncommon and include bleeding and bruising.

Glucose Monitoring Plan:

Guidance for blood glucose monitoring in patients enrolled in the CITRIS-AH Trial:

Ascorbic acid is known to artefactually raise POC blood glucose readings by all POC devices except the StatStrip glucometer. However, it does not raise blood glucose readings from a basic metabolic panel or glucose results using the gas lab. Thus, extreme care must be taken to assure an accurate blood glucose level from a metabolic laboratory (BMP) or arterial blood gas panel before initiating any insulin therapy, including sliding scale or scheduled insulin.

Inpatient units not using the StatStrip POC glucometer should follow the guidelines below.

Guidance for blood glucose monitoring in patients enrolled this study:

- Critical care and Inpatient Unit (Main 9 West) Nursing and Physician leadership at all study sites must be informed of vitamin C’s effect on point of care (glucometer) blood glucose and arterial blood gas glucose point of care values.
- In-service training will be documented in the Study Training Log
- Bold signage will be displayed on all study instructions, data collection forms, and at the patient’s head of bed, stating:
 - ❖ STOP! Do not use Accucheck or other Point of Care devices to measure glucose on this patient
 - ❖ Use only metabolic or gas lab glucose screening methods
 - ❖ This patient is enrolled in a study with Vitamin C, which artefactually increases POC glucose testing
 - ❖ Do Not Initiate or Utilize Sliding Scale, Scheduled Insulin, or Continuous Insulin Infusion Without Laboratory Confirmation of Blood Glucose
- Those receiving insulin infusion or sliding scale insulin as a part of standard of care will have metabolic glucose screening on the schedule determined by the attending physician

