2. Suspected or proven infection: (e.g., thorax, urinary tract, abdomen, skin, sinuses, central venous catheters, and central nervous system.)
3. The presence of a systemic inflammatory response: Defined as: fever: >38°C (any route) or hypothermia: <36°C (core temp only), tachycardia: heart rate > 90 beats/min or receiving medications that slow heart rate or paced rhythm, leukocytosis: >12,000 WBC/μL or leukopenia: <4,000 WBC/μL or >10% band forms. Respiratory rate > 20 breaths per minute or PaCO₂ < 32 or invasive mechanical ventilation.
4. The presence of sepsis associated organ dysfunction as assessed by SOFA: (any of the following thought to be due to infection)
 - a. Sepsis associated hypotension (systolic blood pressure (SBP) < 90 mm Hg or an SBP decrease > 40 mm Hg unexplained by other causes or use of vasopressors for blood pressure support (epinephrine, norepinephrine, dopamine =/> 5mcg, phenylephrine)
 - b. Arterial hypoxemia (PaO₂/FiO₂ ≤ 300) or supplemental O₂ > 6LPM.

- c. Lactate > upper limits of normal laboratory results
 - d. Urine output < 0.5 ml/kg/hour for > two hours despite adequate fluid resuscitation
 - e. Platelet count < 100,000 per mL
 - f. Coagulopathy (INR > 1.5)
 - g. Bilirubin > 2 mg/dL
 - h. Glasgow Coma Scale < 11 or a positive CAM ICU score
5. Negative urine or serum toxicology and acetaminophen drug screen

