6.1.2 DOSING AND ADMINISTRATION

- 1) **First study drug dose** (L-ascorbic acid or placebo) will be considered “Dose 1” and will be administered within 6 hours of randomization or the earliest available time post any clinically indicated procedure which requires the patient to be off the unit. All doses will be administered in the medicine M9W inpatient unit or ICU. Patients receiving vitamin C will receive 25% of the total daily calculated dosing (200mg/kg/24 hours) and will be infused over 30 minutes for this first dosing.
- 2) **Subsequent doses** which represent 25% of the day’s total dose will be infused every six hours through 96 hours (+/- 3 hours).
 - a) Timing of Dose 2 will be triggered by the physician order for q 6 hour administration and will therefore be listed on the bedside MAR. As such, timing of Dose 2 may be out of the +/- 3 hour window and will not trigger a protocol deviation.
 - b) If for any reason any other maintenance dose is not administered within window, the dose will be skipped and the next scheduled dose will be given and documented in the data collection tool.

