According to the Belmont Report, respect for persons incorporates at least two ethical convictions; first, that individuals should be treated as autonomous agents, and second, that persons with diminished autonomy are entitled to protection. One method that serves to protect subjects is restrictions on the participation of subjects in research that presents more than minimal risks. Commentators and Research Ethics Commission have held the view that it is permissible to include incapable subjects in research that involves more than minimal risk as long as there is the potential for beneficial effects and if the research presents a balance of risks and expected direct benefits similar to that available in the clinical setting. Several U.S. task forces have deemed it is permissible to include incapable subjects in research. For example, the American College of Physicians' document allows surrogates to consent to research involving incapable subjects only "if the net additional risks of participation are not substantially greater than the risks of standard treatment." Finally, the National Bioethics Advisory Committee (NBAC) stated "that an IRB may approve a protocol that presents greater than minimal risk but offers the prospect of direct medical benefits to the subject, provided that...the potential subject's LAR gives permission..."

Consistent with the above ethical sensibilities regarding the participation of decisionally incapable subjects in research and the previous assessment of risks and benefits in the previous section, the present trial presents a balance of risks and potential direct benefits that is similar to that available in the clinical setting, with the exception of the additional blood draws.

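### For doses 3–16, section 6.1.1 allows a delay of up to 6 hours that 6.1.2(2)(b) forbids beyond 3 hours, and 6.1.1 leaves room for a central line placed only for study drug

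*Combined protocol and SAP*

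**What the plan says.** Section 6.1.1 opens by addressing every study drug dose. If no line is free when a dose is due, pharmacy is asked whether the dose can be piggybacked. If it cannot, "study drug infusion may be delayed by a maximum of 6 hours". If the clinical drug schedule offers no slot even then, "a dedicated new line (peripheral or central) should be inserted".

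Section 6.1.2 sets the timing rules:

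- Dose 1 has its own limit of 6 hours from randomization, or the earliest time after a clinically indicated procedure off the unit.
- Later doses follow every 6 hours, within ±3 hours.
- Item (a) exempts one dose: "timing of Dose 2 may be out of the +/- 3 hour window and will not trigger a protocol deviation".
- Item (b) covers the rest: "If for any reason any other maintenance dose is not administered within window, the dose will be skipped", and the next scheduled dose is given.

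Neither section refers to the other.

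On risk, section 2.3.1 describes access-related harm only for blood sampling: "Risks of drawing blood percutaneously are uncommon and include bleeding and bruising". Section 10.1.1.2 calls the trial's balance of risks and benefits "similar to that available in the clinical setting, with the exception of the additional blood draws". The organ-dysfunction criteria in section 5.1 include "Platelet count < 100,000 per mL" and "Coagulopathy (INR > 1.5".

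**The concern.** Two sections that bedside staff must follow give different instructions for the same event. Suppose Dose 7 is four hours late because the only line is in use. One nurse can give it under 6.1.1; another must skip it under 6.1.2(2)(b). Dose timing and deviation records would then differ between patients for no clinical reason.

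This reaches the analysis. Section 9.3 makes the per-protocol set the primary analysis for all outcomes and defines it only by sufficient compliance. With 10 patients per arm (section 9.2), moving one patient in or out changes an arm by 1/10 = 10%.

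The second issue is safety. The 6.1.1 wording names a central line as an acceptable response to a scheduling problem created by the study drug. Some patients would face that procedure to receive placebo.

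**Working it through.** **Inputs.** 200 mg/kg per 24 hours in four equal infusions, every 6 hours, 16 doses (sections 4.1 and 6.1.2); ±3 hour window (6.1.2); maximum delay of 6 hours (6.1.1).

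**The plan's dose count.** 96 h / 6 h = 16, which reproduces the stated figure.

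**Is ±3 hours a per-dose window?** The sentence could be read as attaching it to hour 96 alone. Item (a) applies it to Dose 2, so it is per dose.

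**Which doses are in conflict?** Dose 1 has its own rule and Dose 2 is exempt: 16 − 2 = 14 doses, numbers 3 to 16.

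**Timing.** Taking Dose 1 as hour 0, dose k is due at 6(k − 1). Its window closes at 6(k − 1) + 3, and 6.1.1 permits it until 6(k − 1) + 6.

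| Dose | Due (h) | Window, 6.1.2 (h) | Latest, 6.1.1 (h) | Next dose due (h) |
|---|---|---|---|---|
| 3 | 12 | 9–15 | 18 | 18 |
| 7 | 36 | 33–39 | 42 | 42 |
| 15 | 84 | 81–87 | 90 | 90 |
| 16 | 90 | 87–93 | 96 | none |

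The contested period is 6 − 3 = 3 hours per dose.

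**Overlap with the next dose.** A dose given t hours late, with 3 < t ≤ 6, falls 6 − t hours before the next one, that is, from 0 to just under 3 hours before it. That is inside the next dose's window, and at t = 6 it is on its scheduled time. This applies to doses 3–15, or 13 doses. No text says whether such an infusion counts as the late dose or as the next one given early.

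**Exposure.** Each dose is 200/4 = 50 mg/kg and the course is 16 × 50 = 800 mg/kg, so one dose is 50/800 = 6.25%. Skipping loses this relative to 6.1.1 only if the late dose would have been given in addition to the next one. If it would have replaced the next one, total exposure is the same. The documents do not give the frequency. Assuming 1, 2 or 4 doses are lost in a patient, exposure is 750/800 = 93.75%, 700/800 = 87.5% or 600/800 = 75% of the course.

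**Who could receive a study-only line?** Two of the eight organ-dysfunction criteria in section 5.1 are low platelets and raised INR. None of the 20 exclusions in section 5.2 sets an INR or platelet limit. The bleeding exclusions (uncontrolled gastrointestinal bleeding, variceal bleeding within 3 months) do not address coagulopathy.

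**Does section 7.1 settle it?** No. It stops infusions when access is lost. The piggyback step in 6.1.1 concerns a line that is present but in use.

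**The case against.** The best reply is that 6.1.2(2)(b) already decides the matter. It applies whatever the cause, and an occupied line is a cause. On that reading the skip rule governs doses 3–16, while the 6-hour allowance still has a role for Doses 1 and 2. This largely stands as the better reading. But 6.1.1 is written for all doses, and nothing tells staff that its allowance stops after Dose 2.

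A second reply is that the line instruction describes a continuing access problem, so a new line would serve later doses as well. This stands. A reader might infer that the instruction is pointless because the dose has already been skipped, or that skipping always costs just one dose. The documents support neither: if the schedule stays full, skipping repeats.

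A third reply is that harm is remote. It needs no free line, no piggyback option, no slot for a 30-minute infusion, and then a choice of central over peripheral access. That also stands. The inclusion list shows that patients with coagulopathy can enter, not how many will. Every qualifying patient has bilirubin above 3 mg/dL, already past the organ-dysfunction threshold of 2 mg/dL, so INR or platelets need not be the qualifying item.

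A reader might also infer that the overlap with the next dose affects all 14 doses, or that participants are not told about line placement. The first is wrong because there is no Dose 17. The second cannot be judged because the consent form is not available; only the protocol's own risk text is at issue.

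**Conclusion.** The inconsistency is real and should be corrected. It affects doses 3–16 through a 3-hour contested period per dose, and for doses 3–15 it also leaves the identity of a late infusion unclear. The wording of the skip rule suggests that it should prevail, but the protocol does not say so.

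The protocol also permits a central line placed solely for study drug or placebo in patients who may be prone to bleeding, and its risk text does not cover this. It does not require a central line, and clinicians may choose a peripheral one.

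The conclusion rests on reading ±3 hours as a per-dose window, which item (a) supports. How often the situation would arise is not stated, so neither the number of affected doses nor the number of lines can be estimated. The 6.25% per dose is an upper limit on exposure lost by skipping that dose, not an expected effect.

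**What to change.** Amend section 6.1.1 in substance as follows:

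- If piggybacking is ruled out, doses 3–16 may be delayed only within the ±3 hour window. A dose not given by then is skipped under 6.1.2(2)(b), and the next scheduled dose is given.
- Doses 1 and 2 keep their present timing rules.
- For all doses, if the clinical drug schedule leaves no slot for this or later doses, a peripheral cannula may be placed if the treating physician agrees. No central line is placed solely for study drug.

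Add study-only peripheral cannulation to the risk text in 2.3.1 and to the risk-balance sentence in 10.1.1.2.

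The timing change reduces the contested period from 3 hours per dose to 0. The central-line ban is a separate safety choice and is not needed to reconcile the windows.

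The cost is one amended paragraph and two lines of risk text, plus up to 50 mg/kg for each skipped dose that would otherwise have been given in addition to the next one. Several doses may be lost if access stays occupied and no cannula is placed. Because skipped doses may affect who counts as compliant, section 9.3 should state how they are treated in the per-protocol set.

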6.1.2 DOSING AND ADMINISTRATION

- 1) **First study drug dose** (L-ascorbic acid or placebo) will be considered “Dose 1” and will be administered within 6 hours of randomization or the earliest available time post any clinically indicated procedure which requires the patient to be off the unit. All doses will be administered in the medicine M9W inpatient unit or ICU. Patients receiving vitamin C will receive 25% of the total daily calculated dosing (200mg/kg/24 hours) and will be infused over 30 minutes for this first dosing.
- 2) **Subsequent doses** which represent 25% of the day’s total dose will be infused every six hours through 96 hours (+/- 3 hours).
 - a) Timing of Dose 2 will be triggered by the physician order for q 6 hour administration and will therefore be listed on the bedside MAR. As such, timing of Dose 2 may be out of the +/- 3 hour window and will not trigger a protocol deviation.
 - b) If for any reason any other maintenance dose is not administered within window, the dose will be skipped and the next scheduled dose will be given and documented in the data collection tool.

6.2 PREPARATION/HANDLING/STORAGE/ACCOUNTABILITY

6.2.1 ACQUISITION AND ACCOUNTABILITY

VCU Investigational Drug Services (IDS) Pharmacy will coordinate acquisition of sterile L-ascorbic acid for infusion from the manufacturer.

6.2.2 FORMULATION, APPEARANCE, PACKAGING, AND LABELING

ASCOR vials contain 25,000 mg/50mL of ascorbic acid and is supplied as pharmacy bulk packaging (PBP). The diluted ASCOR solution should appear colorless to pale yellow. Amber shrouding will be used to cover the IV bag. The product labeling will be blinded as to what the actual product is. For example, the drug name and dose will be indicated as per the following: "Caution: New Drug—Limited by Federal (or United States) law to investigational use. Ascorbic acid ____mg or placebo in 50cc D5W". The placebo is a 50 mL bag of 5% dextrose in water.

6.2.3 PRODUCT STORAGE AND STABILITY

ASCOR is light sensitive so light exposure should be minimized and stored per package insert instructions:

Store under refrigeration (2°C to 8°C); protect from light with amber IV bag cover. Infusion solutions prepared by the IDS Pharmacy in the Main Pharmacy IV admixture suite will expire in 24 hours if refrigerated and light-protected. Infusion solutions prepared by the ICU Pharmacy after-hours will expire in 12 hours, if refrigerated and light-protected.

There is published data establishing the stability of admixtures of ascorbic acid to be at least 24 hours stored at room temperature or refrigerated. Also, [name] has unpublished data that was obtained prior to an earlier IND trial (IND #113856) which demonstrates the stability of samples prepared in the same manner as described below.

In the event that amber tubing is not available in hospital pharmacy stock (due to shortage or supply chain delays), clear infusion tubing may be used. The manufacturer of ASCOR has unpublished stability data showing minimal product oxidation for up to 96 hours when exposed to ambient light.

6.2.4 PREPARATION

IDS or ICU (after hours) Pharmacy will mix “study drug” or placebo once every 24 hours in four 50 ml hooded infusion bags and stored in the M9W unit or ICU in the dark at 4°C. The prepared IV bags will have the IV tubing attached and primed by *the bedside (M9W or ICU) nursing staff*. At designated infusion time, M9W or ICU Nursing will infuse the contents of the light-shielded agent via infusion pump through light-shielded tubing over 30 minutes. Prior studies performed at VCUHS have shown that L-ascorbic acid prepared for infusion in this way remains stable with no quantifiable oxidation.

Study drug / placebo will be prepared in 50 ml D5W bags, USP, using aseptic technique according to USP 797 requirements. All ASCOR pharmacy bulk package vials utilized will be discarded within 4 hours or sooner as per the ASCOR package insert.

For ascorbic acid, the volume of ascorbic acid to be added to the IV bag will be calculated. This same amount of fluid will be drawn out of the D5W 50 mL bag and discarded. Then, the calculated volume of ascorbic acid will be added to the IV bag. As much air as possible will be removed from the IV bag using an empty syringe with needle attached (in order to prevent oxidation). The IV bag will be covered with a light-protective shroud.

For placebo, a 50cc bag of dextrose 5% in water will have the excess air removed from the IV bag as for the ascorbic acid bags (to maintain the blind). The IV bag will be covered with a light-protective shroud (to maintain the blind).

Microbiologic Controls:

Main Pharmacy IV sterile admixture suite consists of an ISO Class 5 open architecture compounding workbench, with an ISO Class 7 positive pressure buffer zone, and an ISO Class 8 positive pressure anteroom. There is continuous monitoring of temperature, humidity, and air pressure. The environmental controls are recertified every 6 months, including viable active air samples. The pharmacy staff monitors monthly surface samples. Compounding personnel must successfully complete media fill testing and gloved, fingertip sampling as per USP 797 regulations. The ICU Pharmacy (used for after-hours dispensing) has an ISO Class 5 laminar airflow hood (Nuair Class II Type A2 biological safety cabinet) in a segregated compounding area. This biological safety cabinet is recertified every 6 months. ICU compounding personnel must successfully complete media fill testing and gloved, finger-tip sampling as per USP 797 regulations.

